## 1. INTRODUCTION

This Phase 1/2, first-in-human clinical trial is comprised of two study protocols: VC02-101 and VC02-102. It will assess whether VC-02 can be implanted and maintained safely for up to two years in type 1 diabetes mellitus (T1DM) subjects with hypoglycemia unawareness (HU) in VC02-101, and for up to four months in otherwise healthy T1DM subjects in VC02-102. During the first three to six months, VC-02 is expected to vascularize adequately, and pancreatic progenitor cells are expected to differentiate into mature glucose-responsive, insulin-producing cells, capable of secreting insulin in response to serum glucose levels.

Diabetes mellitus, defined by the loss of metabolic glycemic control, is a tremendous healthcare issue. While exogenous pharmaceutical insulin and adjunct medicines can alleviate hyperglycemia, and when managed properly, prevent serious life-threatening excursions in blood glucose levels, it is far from a perfect solution. The natural history of T1DM presents acute and chronic health risks to all affected patients. Controlling the disease with insulin self-administration carries the acute risk of hypoglycemic events (HE) and even death, and the need for constant vigilance and testing results in a significant degradation of quality of life for the patient (and often, their families). Moreover, controlling the short-term challenges of diabetes with monitoring and insulin does not prevent the serious long-term sequelae of diabetes. These long-term sequelae include microvascular complications, such as peripheral and autonomic neuropathies, nephropathies, retinopathy, and diminished wound healing, as well as macrovascular complications and cardiovascular disease.

ViaCyte, Inc. is developing islet replacement therapies to treat diabetes, especially T1DM. A central focus of ViaCyte's overall strategy is utilization of a candidate somatic cell therapy comprised of pancreatic endoderm cells (PEC-01) differentiated from human embryonic stem cell (hESC) that in nonclinical studies mature into pancreatic endocrine hormone-producing cells, including glucose-responsive, insulin-producing cells following subcutaneous implantation. The direct use of PEC-01 may provide an important alternative to the use of cadaver islets in T1DM subjects in which use of immunosuppression is justified. ViaCyte is developing a combination product for delivery of PEC-01 cells to the patient subcutaneously in the presence of immunosuppressive therapy as a potential treatment for high-risk patients with T1DM.

This product candidate, called VC-02 combination product (VC-02), is comprised of PEC-01 loaded in a Delivery Device (DD) with a membrane containing holes of controlled diameter and density designed to deliver and retain cells at the local implant site. The DD provides a means for maintaining the acute cell survival benefit provided by macroencapsulation while still permitting direct host vascularization of the graft. The holes will be large enough to allow capillary ingrowth, yet provide substantial retention of the cell product and thus facilitate formulation, delivery, and ultimate retrieval of the cells through explant of the combination product including the device and associated tissue capsule.

Islet replacement can control blood glucose in a more biological and homeostatic manner than injectable pharmaceuticals, including the various forms of insulin currently on the market, thus reducing or eliminating the blood glucose excursion extremes that plague current therapy. In addition, by providing a more physiologic form of insulin (i.e., pro-insulin, as opposed to exogenous insulin injections), this treatment would also restore C-peptide, which has been reported to alleviate and/or prevent diabetic microvascular complications, such as neuropathy and nephropathy (Wahren, Kallas, & Simas, 2012). If found to be safe and effective, an islet

replacement product may prevent not only the short-term dangers of glycemic excursions, which can result in severe hypoglycemic events (SHE) and diabetic ketoacidosis, but also the long-term effects of the disease and current treatments. In addition, islet replacement therapy has the potential to vastly improve the quality of life for patients with T1DM.

Importantly, due to its stem cell-derived nature, VC-02 overcomes the limitations associated with use of deceased organ donors, which are principally: (1) severely limited supply of suitable cadaveric islets relative to the demand, and (2) patient risks associated with donated organs (e.g., donor-derived pathogens). Moreover, the delivery device, subcutaneous implantation route, and use of PEC-01 provide several advantages over current clinical islet transplantation, including:

- The ability to non-invasively monitor and image the graft site with conventional imaging modalities;
- A single, subcutaneous implantation procedure with the potential of delivering therapeutic benefit equivalent in duration and efficacy to islet transplants which in comparison often require multiple infusion procedures;
- Subsequent explant of the grafted device, allowing for biopsy and histological evaluation;
- Elimination of portal thrombotic events;
- Decreased risk of the deleterious effects on islets associated with instant blood mediated inflammatory reaction; and
- The potential for lower doses of required immunosuppressive drugs, thus decreasing the risk of adverse events, due to the hypo-immunogeneic nature of PEC-01 (Drukker, et al., 2006).

In summary, if the benefits of VC-02, as demonstrated in nonclinical studies, are realized in human trials, this product could deliver an essentially unlimited supply of robust and highly effective cells and could become a dramatically life-changing therapy for high-risk T1DM patients.

This document details the statistical methods planned to perform the interim and final analyses of Protocols VC02-101 and VC02-102.

#### 2. OBJECTIVES AND ENDPOINTS

#### 2.1 Objectives

#### 2.1.1 **Primary Objective**

There are two distinct cohorts in this first in human (FIH) trial, and the cohorts serve different objectives.

VC02-101 Cohort 1 Study Objectives:

- Assess the local and systemic safety and tolerability of VC-02 combination product when implanted into subjects with T1DM and HU.
- Assess histological proof of mechanism for VC-02 combination product (e.g., cell survival and differentiation to beta cells).

## VC02-102 Cohort 1 Study Objectives:

- Assess the local and systemic safety and tolerability of VC-02 combination product when implanted into subjects with T1DM.
- Assess histological proof of mechanism for VC-02 combination product (e.g., cell survival and differentiation to beta cells).

## VC02-101 Cohort 2 Study Objectives:

- Evaluate the clinical efficacy and further assess safety and tolerability of VC-02 combination product from implantation to Month 24.
- Explore effects of weight, gender, body mass index (BMI), or other potentially interacting factors on the responsiveness of the subjects to the experimental intervention.

## 2.1.2 Exploratory Objectives

VC02-101 and VC02-102 - Cohort 1 and 2 Study Objectives:

- Optimize the recommended surgical implantation procedure, anatomical location, and perioperative care for VC-02.
- Assess the effects of the host immune response to implanted VC-02 units.

#### 2.2 Endpoints

#### 2.2.1 Primary Endpoint

#### VC02-101 and VC02-102 Primary Endpoint / Cohort 1:

- Targeted safety and tolerability profile, inclusive of:
  - The incidence of adverse events (AEs) with causality related to VC-02 combination product, the surgical procedures required for VC-02 administration, and the immunosuppressive drug regimen.
  - The incidence of off-target growth as evidenced by implanted VC-02 units via lumen ultrasound measurements, or by histological examination of explants.
  - The incidence of confirmed immune sensitization defined by presence of donor anti-human leukocyte antigen (HLA) antibodies absent prior to implant in conjunction with either confirmatory histological observations from at least one explanted unit and/or the presence of clinical symptoms.
  - Implant tolerability assessments (e.g., fever, erythema, pain, tenderness, induration) for up to four hours post-implantation and at subsequent visits.

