#### 2.2.1. Primary Endpoint Measures

Primary Endpoint / Cohort 1:

- Targeted safety and tolerability profile, inclusive of:
  - The incidence of AEs with causality related to VC-02 combination product, the surgical procedures required for VC-02 administration, and the immunosuppressive drug regimen.
  - The incidence of off-target growth as evidenced by implanted VC-02 units via lumen ultrasound measurements, or by histological examination of explants.
  - The incidence of immune sensitization defined by presence of donor anti-HLA antibodies absent prior to implant.

- Implant tolerability assessments (e.g., fever, erythema, pain, tenderness, induration) for up to four hours post-implantation and at subsequent visits.

Primary Endpoint / Cohort 2:

• Change from baseline to Week 26 in C-peptide AUC0-4h following an MMTT.

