### 8.1.3. Determination of Abnormal Laboratory Test Values or Abnormal Clinical Findings as Adverse Event

The criteria for determining whether an abnormal, objective test finding should be reported as an AE are as follows:

- Test result is associated with accompanying symptoms, and/or
- Test result is not associated with a known, pre-existing condition or part of the subject's medical history, and/or
- Test result requires additional diagnostic testing or medical/surgical intervention, and/or
- Test result leads to discontinuation from the study, significant additional concomitant drug treatment, or other therapy, and/or
- Test result is considered to be an AE by the Investigator or sponsor.

Merely repeating an abnormal test, in the absence of any of the above conditions, does not constitute an AE. An abnormal test result determined to be an error does not require reporting as an AE.

Evidence of product sensitization (the presence of donor anti-HLA antibodies absent prior to implant) is not in itself considered an AE. The above criteria should also be utilized to determine if the sensitization qualifies as an AE.

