# **10. STATISTICAL CONSIDERATIONS**

Methodology for the summarization and analysis of the data collected in this trial are given here and further detailed in a SAP, which will be maintained by the Sponsor. The SAP may be written and approved prior to the Cohort 1 data cut-off (e.g., the last subject in Cohort 1 completing the Week 4 visit whose data is part of the DSMB data review), since this time-point will trigger a DSMB review of the accumulated data and result in a recommendation for enrollment of Cohort 2.

The study SAP may modify what is outlined in the protocol; however, any major modifications of the endpoints or their analyses will be reflected in a protocol amendment.

The phrase "treatment group" is used in this section to denote the number of initially implanted VC-02-300 units. If a subject has a VC-02-300 unit explanted for any reason and remains in the study, then he/she will be included in the treatment group that is described by the number of VC-02-300 units originally implanted. If no VC-02-300 units are implanted, but sentinel units are implanted, then the subject will be included in the "0 implanted VC-02-300 units" treatment group.

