## **SAP Revisions**

Version 1.0 of the SAP was finalized at the time of Protocol VC02-101 version 2.0 (28JUL2017) and Protocol VC02-102 (27APR2017). The following table details the changes made to the SAP due to subsequent protocol amendments.

Protocol			
Version #	SAP Section		Description on d Detionals
Date   8.0   (Amendment   #9)   18 May 2020	Section 2.1.1	Modification Removed "to Month 4" from the first bulleted study objective of VC02-101 Cohort 1 and VC02- 102 Cohort 1.	Description and Rationale Safety data is collected through Week 104. This language will be removed in subsequent protocol amendments.
8.0 (Amendment #9) 18 May 2020	2.2.1	Removed "to Month 4" from the Primary Endpoint of VC02-101 Cohort 1 and VC02-102 Cohort 1.	Safety data is collected through Week 104. This language will be removed in subsequent protocol amendments.
		Added "confirmed" to immune sensitization to third sub bullet within the VC02-101 and VC02- 102 Primary Endpoint for Cohort 1. Revised definition of confirmed immune sensitization to include "confirmatory histological observations from at least one explanted unit and/or the presence of clinical symptoms" to third sub bullet within the VC02-101 and VC02-102 Primary Endpoint for Cohort 1.	Language updated by Sponsor, and will be updated in subsequent protocol amendments. Language updated by Sponsor, and will be updated in subsequent protocol amendments.
8.0 (Amendment #9) 18 May 2020	2.2.2	Added "confirmed" to immune sensitization to the Safety and Tolerability Endpoints for VC02- 101.	Language updated by Sponsor, and will be updated in subsequent protocol amendments.
		Revised definition of confirmed immune sensitization to include "confirmatory histological observations from at least one explanted unit and/or the presence of clinical symptoms" to the Safety and Tolerability Endpoints for VC02-101.	Language updated by Sponsor, and will be updated in subsequent protocol amendments. Language updated by Sponsor, and

Protocol			
Version #	SAP	3 A 1 0 1	
Date	Section	Modification	Description and Rationale
		Added Weeks 8, 12, 20, 65, and 91 to the first secondary efficacy endpoint for VC02-101.	will be updated in subsequent protocol amendments.

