#### *VC02-101*:

The comprehensive safety profile of VC-02 combination product implanted for up to two years as measured by:

- All reported AEs
  - The incidence of confirmed immune sensitization defined by presence of donor anti-HLA antibodies absent prior to implant in conjunction with either confirmatory histological observations from at least one explanted unit and/or the presence of clinical symptoms.
- Implant tolerability assessments (e.g., fever, erythema, pain, tenderness, induration) for up to four hours post-implantation and at subsequent visits.
- The incidence of subjects requiring a premature explant due to safety, tolerability, or malfunction issues.

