#### 7.3.7 Immune Panel

A listing of immune panel tests will be provided. The panel of immune function tests include:

- Humoral alloreactivity measured via human leukocyte antigen panel reactive antibody (HLA-PRA)
- Humoral autoimmunity measured via T1DM autoantibody titers of glutamate decarboxylase antibodies (GADA), insulin antibodies (IAA), islet antigen-2 antibodies (IA2A), and zinc transporter 8 (ZnT8)
- Cellular alloreactivity measured via mixed lymphocyte reaction (MLR)
- Cellular autoimmunity measured via lymphocyte stimulation test (LST)
- Cellular autoimmunity measured via Diab-Q Kit
- HLA typing of each subject (required to interpret the cellular immunity test results)

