#### 7.6.2 Immune Sensitization

The number and percentage of subjects enrolled in VC02-101 Cohort 1 with confirmed immune sensitization defined by presence of donor anti-HLA antibodies absent prior to implant in conjunction with either confirmatory histological observations from at least one explanted unit and/or the presence of clinical symptoms will be summarized by cohort and treatment group.

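### The SAP counts immune sensitization more narrowly than the protocol, so the protocol's endpoint incidence may be under-reported and has no committed table

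*SAP*

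**What the plan says.** **Protocol.** Section 2.2.1 lists this component of the Cohort 1 primary endpoint: "The incidence of immune sensitization defined by presence of donor anti-HLA antibodies absent prior to implant". Section 2.2.2 repeats the definition as a secondary safety endpoint, and the Protocol Summary does the same. None of these places mentions histology or symptoms.

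**SAP.** Section 2.2.1 requires the antibodies "in conjunction with either confirmatory histological observations from at least one explanted unit and/or the presence of clinical symptoms". Section 2.2.2 carries the same definition into the VC02-101 secondary safety endpoint: "The incidence of confirmed immune sensitization defined by presence of donor anti-HLA antibodies absent prior to implant in conjunction with either confirmatory histological observations", with clinical symptoms as the other route. Sections 7 and 7.6.2 use it again.

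**Outputs.** SAP 7.6.2 commits to one count: "The number and percentage of subjects enrolled in VC02-101 Cohort 1 with confirmed immune sensitization". For the immune panel, which includes the HLA panel reactive antibody assay, SAP 7.3.7 says: "A listing of immune panel tests will be provided". SAP 7 promises a narrative for confirmed cases and leaves any summary of assay data optional.

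**Adverse event status.** Protocol 8.1.3 states: "Evidence of product sensitization (the presence of donor anti-HLA antibodies absent prior to implant) is not in itself considered an AE". It then says that the general criteria for abnormal tests decide whether a given case qualifies.

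**Process.** Protocol section 10 lets the SAP modify the protocol's outline, but adds that "any major modifications of the endpoints or their analyses will be reflected in a protocol amendment". The SAP's revision table discloses the new definition and gives as its rationale: "Language updated by Sponsor, and will be updated in subsequent protocol amendments".

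**The concern.** Two documents in force at the same time give different case definitions for a named component of a primary safety endpoint. An analyst who follows the SAP will report a different quantity from the one the protocol promises, and the difference can run only towards fewer cases.

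The protocol's own risk section (1.4.1) says that sensitization may limit a subject's candidacy for a later islet transplant. Since the protocol defines sensitization by antibodies alone, a subject with new antibodies but no symptoms and no histological finding falls within that stated risk. The step from definition to risk is an inference, because 1.4.1 does not spell out the mechanism. Such a subject is nevertheless absent from the only sensitization count that the SAP commits to produce. In a first-in-human trial, that incidence is among the things the primary endpoint was set up to describe.

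**Working it through.** The plan states no expected rate, power or test for sensitization: the size of Cohort 1 is empirical and no hypotheses are tested. There is no figure to reproduce. The check is a comparison of definitions, then an illustration on assumed rates.

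**1. The two counts.** Let A be the subjects with new donor anti-HLA antibodies, H those with confirmatory histology in at least one explanted unit, and S those with clinical symptoms.

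- Protocol count = |A|
- SAP count = |A ∩ (H ∪ S)| ≤ |A|
- Difference = the members of A who are in neither H nor S (antibody-only cases)

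The counts agree only if every antibody-positive subject also has histology or symptoms.

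**2. Where an antibody-only case can appear.**

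| Output | Included? |
|---|---|
| SAP 7.6.2 number and percentage | No: confirmed cases only |
| SAP 7.3.7 immune panel listing | Yes, as individual results |
| SAP 7 assay summary | At discretion; no variable or count defined |
| SAP 7.2.7 TEAE tables | Only if judged an adverse event under Protocol 8.1.3 |

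**3. Which groups the committed count covers.** SAP 2.2.1 names the component for Cohort 1 of both VC02-101 and VC02-102. SAP 2.2.2 names it as a secondary endpoint for VC02-101 without limiting it to one cohort. SAP 7.6.2 counts VC02-101 Cohort 1 only. So Cohort 2 and VC02-102 have no committed count even of confirmed cases.

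**4. Illustration, n = 15 (the Cohort 1 maximum).** Let p be the antibody incidence and s the share of antibody-positive subjects who have neither histology nor symptoms. Both are assumptions.

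- Expected cases: protocol 15p; SAP 15p(1 − s)
- Chance of at least one case: protocol 1 − (1 − p)^15; SAP 1 − (1 − p(1 − s))^15

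| p | Protocol: expected; P(≥1) | SAP, s = 25% | s = 50% | s = 75% | s = 100% |
|---|---|---|---|---|---|
| 10% | 1.5; 0.794 | 1.13; 0.689 | 0.75; 0.537 | 0.38; 0.316 | 0; 0 |
| 20% | 3.0; 0.965 | 2.25; 0.913 | 1.5; 0.794 | 0.75; 0.537 | 0; 0 |
| 40% | 6.0; 1.000 | 4.5; 0.995 | 3.0; 0.965 | 1.5; 0.794 | 0; 0 |

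In observed counts, with exact 95% limits: 4/15 = 26.7% (7.8% to 55.1%) under the protocol definition. If one of the four is confirmed, the SAP reports 1/15 = 6.7% (0.2% to 31.9%). If none is, it reports 0/15 (0% to 21.8%).

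**The case against.** **The cases do not vanish.** A reader might infer that antibody-only sensitization is counted nowhere and drops out of every incidence table. The documents do not support that. The assay results are listed, and with at most 15 subjects in Cohort 1 a reader can search the listing. An assay summary is permitted. Protocol 10.4.5.2 also calls for a narrative on any subject who appears to be having an immune response. Protocol 8.1.3 leaves the adverse event route open, including by the sponsor's own judgment, and a case judged an adverse event after implant would enter the TEAE tables. Protocol 7.11.4 says that sites may not receive immune results, which weakens the investigator's part of that route but not the sponsor's. This objection stands against the stronger reading. It does not supply a committed incidence, which is what the protocol names as the endpoint.

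**Explant timing.** A reader might also infer that the sponsor controls the count through its choice of explant times. That is weak. All remaining units come out at Week 104 or on withdrawal, all explanted units go to histology, one unit is enough, and symptoms alone suffice.

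**Process.** The change is disclosed, and Protocol section 10 does not say that the amendment must come before the SAP. Nor do the documents show that the change was prompted by data. The revision table ties some other items to interim safety summaries, but not this one. What stands is narrower: the current protocol does not contain the definition that the current SAP will use.

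**Consequence.** The endpoint is descriptive, so no error rate or test result is affected.

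**Conclusion.** The concern holds in this form: the two current documents define the same endpoint differently, the SAP's count is a subset of the protocol's, and no planned table is committed to report the protocol's incidence. The protocol's endpoint may therefore be under-reported, by exactly the number of antibody-only cases.

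That number is unknown. It would be zero if every antibody-positive subject also had histology or symptoms. The rates and counts in the illustration are assumptions and predict nothing about this product. The subset relation rests on no assumption beyond the two texts.

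This should be corrected before the analysis is run. It is an inconsistency in a safety endpoint and a gap in tabulation, and the documents do not support calling it concealment.

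**What to change.** 1. In SAP 2.2.1, 2.2.2, 7 and 7.6.2, make the endpoint the number and percentage of subjects with new donor anti-HLA antibodies, as the protocol defines it.
2. Show confirmed sensitization beneath it as a supportive subset row. State what histological findings and what symptoms qualify, since the SAP text gives no criteria for either.
3. Extend the table in SAP 7.6.2 from VC02-101 Cohort 1 to every group for which the SAP names the endpoint: VC02-101 Cohorts 1 and 2, and VC02-102.
4. Reconcile the definitions. Either the SAP returns to the protocol's wording, or the protocol is amended as its section 10 foresees. In either case, keep the antibody row in the table.

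The antibody data are already collected and listed. The cost is SAP wording and an added table row by cohort, plus a protocol amendment only if the sponsor wants the confirmed definition to become the endpoint.
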